# 4.3. Protocol Deviations

A summary will present the number and percentage of subjects who did not meet at least 1 eligibility criterion and the number of subjects who did not meet specific criteria by treatment group and overall based on the Safety Analysis Set. A by-subject listing will be provided for all randomized subjects who violated at least 1 inclusion or exclusion criterion. The listing will include the criteria not met. A listing of subjects who received the wrong study drug will also be provided.

Protocol deviations occurring after subjects entered the study are documented during routine monitoring. The number and percentage of subjects with important protocol deviations by deviation reason and the total number of important protocol deviations by deviation reason (ie, nonadherence to study drug, violation of select inclusion/exclusion criteria) will be summarized by treatment group for the Full Analysis Set. A by-subject listing will be provided for those subjects with important protocol deviation.

## 5. BASELINE CHARACTERISTICS

# 5.1. Demographics and Baseline Characteristics

Subject demographic data and baseline characteristics will be summarized by treatment group and overall using descriptive statistics (n, mean, SD, median, Q1, Q3, minimum, and maximum) for continuous data and by the number and percentage of subjects for categorical data. The following summaries of demographic data and baseline subject characteristics will be provided separately for the Safety Analysis Set:

- Age (years)
- Age categories (years): (a) 18 to < 25, (b)  $\ge 25$  to < 50, (c)  $\ge 50$
- Sex at birth
- MSM or TGW status
- Race: (a) American Indian or Alaska Native, (b) Asian, (c) Black/Mixed Black, (d) Native Hawaiian or Pacific Islander, (e) White, (f) Other (Nonblack), (g) Not Permitted
- Ethnicity: (a) Hispanic, (b) Non-Hispanic, (c) Not Permitted
- Body weight (kg)
- Height (cm)
- Body mass index [BMI] (kg/m^2)
- Selected self-reported demographic factors from the CASI Screening questionnaire, including:
- Male or Transgender Female status
- Sexuality: (a) Gay/homosexual, (b) Straight/heterosexual (c) Bisexual, (d) Other
- Highest level of education: (a) Less than high school, (b) High school/GED,
   (c) Some college, (d) 2-year college/AA, (e) 4-year college, (f) Master's degree, (g) Doctoral degree, (h) Professional degree, (i) Other
- Work situation: (a) Full-time employment (employed or self-employed full-time at least 30 hours a week), (b) Part-time employment (employed or self-employed part-time less than 30 hours a week), (c) Part/full time student/education/training, (d) Unemployed, (e) Retired, (f) Other
- Ongoing relationship with a partner: (a) Yes and living with my partner, (b) Yes but not living with my partner, (c) No
- Circumcised: (a) Yes, (b) No, (c) N/A (Post-Operative)

For categorical data, the Cochran-Mantel-Haenszel (CMH) test (ie, general association statistic for nominal data or row mean score test for ordinal data) will be used to compare the 2 treatment groups. For weight and BMI, an ANOVA test which includes treatment and baseline F/TDF for PrEP as fixed effects will be used to compare the 2 treatment groups. For other continuous data, the 2-sided Wilcoxon rank sum test will be used to compare the 2 treatment groups.

#### 5.2. Baseline Medical Characteristics

Baseline medical characteristics will be summarized by treatment group and overall using descriptive statistics (n, mean, SD, median, Q1, Q3, minimum, and maximum) for continuous data and by the number and percentage of subjects for categorical data. The following summaries of baseline medical characteristics will be provided for the Safety Analysis Set:

- eGFRCG (mL/min)
- HBV infection status (Yes/No/Missing)

Subjects with HBV infection at baseline are defined as subjects meet any of the following two criteria:

Positive HBsAg on or prior to the first dose date, or

Negative HBsAg, negative HBsAb, positive HBcAb, and quantifiable HBV DNA (ie, HBV DNA  $\geq$  20 IU/mL) on or prior to the first dose date.

• HCV infection status (Yes/No/Not Applicable/Missing)

Subjects with HCV infection at baseline are defined as subjects with positive HCVAb or quantifiable HCV RNA (ie, HCV RNA  $\geq$  15 IU/mL) on or prior to the first dose date.

- Hip BMD (g/cm^2) for the Hip DXA Analysis Set
- Spine BMD (g/cm^2) for the Spine DXA Analysis Set
- Urine beta-2-microglobulin to creatinine ratio (ug/g)
- Urine RBP to creatinine ratio (ug/g)
- Serum creatinine (mg/dL)
- Proteinuria toxicity grade by urinalysis (dipstick)

For categorical data, the Cochran-Mantel-Haenszel (CMH) test (ie, general association statistic for nominal data or row mean score test for ordinal data) will be used to compare the 2 treatment groups. For BMD and serum creatinine, an ANOVA test which includes treatment and baseline F/TDF for PrEP as fixed effects will be used to compare the 2 treatment groups. For renal biomarkers and eGFR, a Van Elteren test stratified by baseline F/TDF for PrEP will be used to compare the 2 treatment groups.

### 5.3. Baseline HIV Risk Characteristics

Baseline HIV risk characteristics will be summarized by treatment group and overall using descriptive statistics (n, mean, SD, median, Q1, Q3, minimum, and maximum) for continuous data and by the number and percentage of subjects for categorical data. The following summaries of baseline HIV risk characteristics will be provided separately for the Safety Analysis Set:

- Any prior F/TDF for PrEP (defined in Section 7.6.2)
- Baseline F/TDF for PrEP (defined in Section 7.6.3)
- History of syphilis in the past 24 weeks (from Medical History eCRF)
- History of rectal gonorrhea in the past 24 weeks (from Medical History eCRF)
- History of rectal chlamydia in the past 24 weeks (from Medical History eCRF)
- Chlamydia
- Urine (from central laboratory test)
- Rectal (Nucleic acid amplification test [NAAT] or other local laboratory tests)
- Pharyngeal (NAAT or other local laboratory tests)
- Gonorrhea
- Urine (from central laboratory test)
- Rectal (NAAT or other local laboratory tests)
- Pharyngeal (NAAT or other local laboratory tests)
- Syphilis Diagnosis (Yes/No/Missing) from investigator report

Primary, (b) early latent, (c) secondary, (d) tertiary, (e) late latent, (f) other

New, (b) re-infection, (c) treatment failure

- Selected Screening visit CASI questionnaire responses to be included are:
- Receptive anal intercourse (RAI) partners in 90 days prior to Screening
- Number of partners
- Percentage of subjects in the categories of: 0, 1, 2, 3, 4-5, 6-10 and  $\geq$  11 partners

- Unprotected receptive anal intercourse (URAI) partners in 90 days prior to Screening
- Number of partners
- Percentage of subjects in the categories of: 0, 1, 2, 3, 4-5, 6-10 and  $\geq 11$  partners
- Insertive anal intercourse (IAI) partners in 90 days prior to Screening
- Number of partners
- Percentage of subjects in the categories of: 0, 1, 2, 3, 4-5, 6-10 and  $\ge 11$  partners
- Unprotected insertive anal intercourse (UIAI) partners in 90 days prior to Screening
- Number of partners
- Percentage of subjects in the categories of: 0, 1, 2, 3, 4-5, 6-10 and  $\ge 11$  partners
- Recreational drug use in the last 3 months prior to Screening (Yes/No)
- Frequently ask my partner to use a condom for anal sex to manage risk of getting HIV (Yes/No)
- Frequently use condoms to manage risk of getting HIV (Yes/No)
- Prescribed post-exposure prophylaxis for 4 weeks after potential HIV exposure, in the past 12 months prior to Screening
- Number of times prescribed
- Percentage of subjects in the categories of: 0, 1, 2, 3-5, 6-11 and  $\geq$  12 times prescribed
- AUDIT questionnaire total score at screening (defined in Appendix 5)
- AUDIT questionnaire total score at screening categories (a)  $\leq 8$  or (b)  $\geq 8$  to  $\leq 15$  (c)  $\geq 15$
- Selected Screening visit AUDIT questionnaire responses to be included are:
- Frequency of alcohol use (a) Never, (b) Monthly or less, (c) 2 to 4 times a month, (d) 2 to 3 times a week, (e) 4 or more times a week
- Alcohol use on days when subject drank (number of drinks): (a) Frequency of alcohol use Never, (b) 1 or 2, (c) 3 or 4, (d) 5 or 6, (e) 7, 8, or 9, (f) 10 or more
- Six or more drinks on one occasion: (a) Frequency of alcohol use Never (b) Never, (c) Less than monthly, (d) Monthly, (e) Weekly, (f) Daily or almost daily
- Felt guilt or remorse after drinking (during the last year): (a) Frequency of alcohol use Never or [Alcohol use on days when subject drank 1 or 2 and Six or more drinks on one occasion Never] (b) Never, (c) Less than monthly, (d) Monthly, (e) Weekly, (f) Daily or almost daily

For categorical data, the Cochran-Mantel-Haenszel (CMH) test (ie, general association statistic for nominal data or row mean score test for ordinal data) will be used to compare the 2 treatment groups. For continuous data, the 2-sided Wilcoxon rank sum test will be used to compare the 2 treatment groups.

### 5.4. Medical History

General medical history data will be collected at screening and listed only. General medical history data will be coded using the current version of Medical Dictionary for Regulatory Activities (MedDRA).

### 6. EFFICACY ANALYSES

All necessary summaries on the primary efficacy endpoint (when all subjects have a minimum follow-up of 48 weeks and at least 50% of the subjects have 96 weeks of follow-up after randomization or permanently discontinued from the study) have been performed as part of the Primary Analysis CSR, and will not be repeated for this analysis. Only the DB phase data will be summarized.

### 6.1. Primary Efficacy Endpoint

### 6.1.1. Definition of the Primary Efficacy Endpoint

The primary endpoint is the incidence of HIV-1 infection rate per 100 person-years (PY). The primary endpoint will be assessed when all subjects have a minimum follow-up of 48 weeks and at least 50% of the subjects have 96 weeks of follow-up after randomization or permanently discontinued from the study.

The statistical analysis methods for the primary efficacy endpoint were described in the Primary Analysis SAP and the analysis was performed in the Primary Analysis.

### 6.2. Secondary Efficacy Endpoint

### 6.2.1. Definition of the Secondary Efficacy Endpoint

The secondary efficacy endpoint is the incidence of HIV-1 infection rate per 100 person-years (PY) assessed when all subjects have a minimum follow-up of 96 weeks after randomization or permanently discontinued from the study. The HIV-1 infection incidence rate per 100 PY of follow-up will be computed as the number of subjects who became HIV-1 infected during the study after first dose of study drug divided by the sum of all subjects' years (where a year is 365.25 days) of follow-up while at risk of HIV-1 infection during the DB phase study. Follow-up in study while at risk of HIV-1 infection is defined in Section 6.2.3.

[figure not shown]
### 6.2.2. Definition of HIV-1 Infection

HIV-1 infection is defined by one or more of the following criteria of contributing HIV tests performed via central lab or local lab:

- 1) Serologic evidence of seroconversion (reactive screening HIV Antigen/Antibody or Antibody test, confirmed by reactive HIV-1/HIV-2 differentiation assay), or
- 2) Virologic evidence of HIV-1 infection (positive qualitative HIV-1 RNA test or any detectable quantitative HIV-1 RNA test), or
- 3) Evidence of acute HIV-1 infection (reactive p24 Antigen or positive qualitative or quantitative RNA, in the absence of reactive HIV-1 Antibody results)

The flowchart in Figure 6-1 focuses on contributions from the central laboratory and provides a general assessment of contributing HIV tests performed by the central laboratory.

Figure 6-1. General Assessment of Contributing HIV tests Performed by the Central Laboratory

Positive virologic evidence, based on qualitative or quantitative HIV-1 RNA tests, is used for confirmation of HIV-1 infection while other HIV tests are also used to assess the date of diagnosis (ie, HIV infection date for analysis).

Positive virologic evidence is defined as either:

- 1) Qualitative HIV-1 RNA test with positive results or
- 2) Quantitative HIV-1 RNA test with detectable HIV-1 RNA results ("< 20 cp/ml HIV-1 RNA Detected" or any value ≥ 20 copies/mL)

The date of HIV infection diagnosis is assessed by a retrospective look, starting from the date of the first positive virologic evidence, through the preceding test results from other contributing HIV tests (including both Covance and local tests). The look back stops at the first date with negative assessments on all available HIV tests prior to the date of first positive virologic evidence. The date of HIV-1 diagnosis is set at the earliest positive result in the retrospective look process from either an on-site rapid test, a test sent to the central Covance laboratory, or any other provided local test performed outside of the study that documents the presence of HIV infection.

This algorithm excludes diagnosis of HIV-1 infection for vaccinated subjects who may have positive HIV-1 serology but no positive virologic evidence. For HIV vaccinated subjects, the date of HIV infection diagnosis is the date of first positive virologic evidence, based on qualitative or quantitative HIV-1 RNA tests.

### 6.2.3. Definition of Duration of At Risk of HIV Infection in Study

Duration of at risk of HIV infection is defined as the time between Day 1 (first dose date) and the end date (end date Day 1 date +1), where end date is defined as the last at-risk of HIV infection date:

- 1) For subjects who have been diagnosed as infected with HIV during the DB phase: the date of HIV infection diagnosis (as defined in Section 6.2.2)
- 2) For subjects who have not been infected with HIV during the DB phase: the date of the last post-baseline HIV laboratory test (either local HIV or Covance HIV laboratory tests) during the DB phase (may include the 30-day follow-up visit).

Duration of time at risk of HIV infection in study will be summarized using descriptive statistics (n, mean, SD, median, Q1, Q3, minimum, maximum and total person-years) and as the number and percentage of subjects at risk of HIV infection in study for specified periods, ie,  $\geq$  4 weeks (28 days),  $\geq$  8 weeks (56 days),  $\geq$  12 weeks (84 days),  $\geq$  24 weeks (168 days),  $\geq$  36 weeks (252 days),  $\geq$  48 weeks (336 days),  $\geq$  60 weeks (420 days),  $\geq$  72 weeks (504 days),  $\geq$  84 weeks (588 days),  $\geq$  96 weeks (672 days),  $\geq$  108 weeks (756 days),  $\geq$  120 weeks (840 days),  $\geq$  132 weeks (924 days),  $\geq$  144 weeks (840 days), etc.

### 6.2.4. Statistical Hypothesis for the Secondary Efficacy Endpoint

**Null hypothesis:** The HIV infection rate ratio of F/TAF over F/TDF is at least 1.62 or higher.

**Alternative hypothesis:** The HIV infection rate ratio of F/TAF over F/TDF is less than 1.62.

## 6.2.5. Primary Analysis of the Secondary Efficacy Endpoint (HIV Infection Rate Ratio Method)

The analysis purpose of the secondary efficacy endpoint is to assess the noninferiority of treatment with F/TAF relative to treatment with F/TDF via HIV infection rate ratio estimation from a Poisson regression model. Noninferiority will be assessed using a 95% CI constructed using a generalized model associated with a Poisson distribution and logarithmic link with the treatment group being the main effect and a noninferiority margin of 1.62.

It will be concluded that F/TAF is noninferior to F/TDF if the upper bound of the 2-sided 95% CI of the rate ratio (F/TAF group over F/TDF group) of the HIV infection incidence rate is less than 1.62 (Appendix 2).

If noninferiority of F/TAF versus F/TDF is established, the same 95% CI used in evaluating noninferiority will be used to evaluate superiority. If the upper bound of the 95% CI is less than 1, then superiority of F/TAF over F/TDF using the rate ratio estimation is established. The p-value from a Poisson model will also be used to assess superiority as a secondary assessment. The FAS will be used for the secondary efficacy endpoint analysis and the superiority evaluation.

### 6.2.6. Sensitivity Analyses of the Secondary Efficacy Endpoint While On-Treatment (HIV Infection Rate Ratio Method)

A sensitivity analysis of the secondary endpoint will be based on HIV infections occurring while subjects are on-treatment during the double-blinded phase of the study using the PP analysis set. This on-treatment analysis will include HIV infection events and follow-up times occurring between first dose date to DB phase last dose date plus 10 days (for F/TDF) or plus 16 days (for F/TAF) and exclude:

- 1) HIV-1 infection events and follow-up time during the OLE phase.
- 2) Off study drug PrEP (off-treatment) HIV infection events and follow-up time defined as events and follow-up time occurring greater than 10 days for (F/TDF) or 16 days (for F/TAF) after permanent discontinuation of study drug (Appendix 7).
- 3) HIV infections and follow-up time occurring after subjects initiated any non-study PrEP treatment that includes the period after permanent discontinuation of study drug (including commercial drugs like Truvada®, generic Truvada, or investigational drugs like cabotegravir for PrEP with a stop date that is either ongoing or after permanent discontinuation of study drug).

The HIV infection incidence rate per 100 person-years of follow-up will be computed as the number of subjects with on-treatment HIV infection divided by the sum of all subjects' years (where a year is 365.25 days) of on-treatment follow-up while at risk of HIV infection in study. The duration of on-treatment follow-up while at risk of HIV infection is defined as the time between Day 1 (first dose date) and the end date (end date Day 1 date +1) where end date is defined as:

- For subjects who have been diagnosed as infected with HIV while on-treatment: the date of the on-treatment HIV infection which will be the date of the HIV infection diagnosis (as defined in Section 6.2.2).
- 2) For subjects who have not been infected with HIV while on-treatment, the earlier of:
  - a) last dose date + 10 days for F/TDF or + 16 days for F/TAF for subjects who permanently discontinued study drug (including subjects with off-treatment HIV infection)
  - date of last post-baseline HIV laboratory test (either local or Covance HIV laboratory tests, which may include the 30-day follow-up visit date) for subjects who have not permanently discontinued study drug
  - start date of any non-study PrEP treatment that includes the period after permanent discontinuation of study drug (including commercial drugs like Truvada, generic Truvada, or investigational drugs like cabotegravir for PrEP with a stop date that is either ongoing or after permanent discontinuation of study drug)
  - d) the first dose date of the OLE phase if available.

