7.6.6. Potential High-Risk Exposure

For participants who present after a high-risk sexual exposure, were non-adherent to study drug, and request PEP, investigators may discontinue the participant's study medication and provide PEP in accordance with local medical practice and/or guidelines. Participants who complete their PEP regimen and wish to continue on study may resume with study medication following the criteria as detailed in Section 6.8. Participants who present after a high-risk sexual exposure with reported good adherence to study drug do not require PEP.

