In general, permanent discontinuation of study drug refers to premature discontinuation of study drug or completion of study drug and regardless of any gaps in continuous dosing (ie, temporary discontinuation due to adverse event (AE) or subject request after which subjects may resume study drug).

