# 3.8. Analysis Windows

# 3.8.1. Definition of Study Day

**Study Day 1 (DB phase)** is defined as the day when the first dose of randomized study drug (ie, *F/TAF or Placebo-to-match F/TAF*, *F/TDF or Placebo-to-match F/TDF*) was taken, as recorded on the Study Drug Administration eCRF form.

**Study Day 1 (OLE phase).** For subjects who were treated in the OLE phase, Study Day 1 is defined as the day when the first dose of OLE phase study drug (ie, F/TAF) was taken, as recorded on the "Extension Phase" Study Drug Administration eCRF.

**Study Days** are calculated relative to Study Day 1 for each phase. For events that occurred on or after the Study Day 1 date, the number of study days is calculated as (visit date minus Study Day 1 date plus 1). For events that occurred prior to DB phase Study Day 1, the number of study days is calculated as (visit date minus Study Day 1 date).

**Last Dose Date (DB phase)** is the latest of the blinded study drug end dates (administering ≥1 tablet per day) recorded on the Study Drug Administration eCRF form with "Permanently Withdrawn" box checked for subjects who prematurely discontinued or completed study drug in the blinded treatment study phase according to the Study Drug Completion eCRF.

If last dose date is completely missing (ie, due to lost to follow-up) for subjects who prematurely discontinued or completed blinded study drug at the data cut date in the DB phase, the latest of study drug start dates and end dates, the clinic visit dates, and the laboratory visit dates excluding the date of 30-day follow-up visit, from the DB phase data, will be used to impute the DB phase last dose date. For other partial missing last dose date, please see the programming specifications for imputation rule details.

If the DB phase last dose date is after the first dose date of the OLE phase, use the day before the first dose date of the OLE phase to impute it.

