#### 4.2.2. Duration of Study Drug Holidays and Study Drug Interruptions

## 4.2.2.1. Definition of Study Drug Holidays and Study Drug Interruptions

The duration of study drug holidays and study drug interruptions will only be calculated for the randomize phase study drug. Study drug holidays or other study drug interruptions may occur when subjects cease taking study drug either with or without prior notification to the study sponsor and prior to permanently discontinuing study drug. For subjects who notified the study sponsor of their intention to take a study drug holiday and received pre-approval preceding the end of the interruption, records with '0' tablets administered are entered in the Study Drug Administration eCRF. Other study drug interruptions are defined as gaps in consecutive stop and start dates of study drug records with ≥1 tablet administered in the study drug administration eCRF.

During the DB phase, if subjects are on a study drug holiday or other study drug interruption at the time of the data cut date, the latest of study drug start dates and end dates, the clinic visit or laboratory visit dates during the DB phase, excluding the 30-day follow-up visit date, will be used to impute the end of the interruption for the calculation of the duration of study drug holiday or study drug interruption.

For the DB phase, durations of (1) study drug holidays, (2) other study drug interruptions and (3) any study drug interruptions (the cumulative total of both study drug holidays and other study drug interruptions) will be summarized using descriptive statistics (n, mean, SD, median, Q1, Q3, minimum, and maximum) and as the number and percentage of subjects with study drug holidays and/or other study drug interruptions for specified periods, ie,  $\geq$  4 weeks (28 days),  $\geq$  8 weeks (56 days),  $\geq$  12 weeks (84 days),  $\geq$  24 weeks (168 days),  $\geq$  36 weeks (252 days),  $\geq$  48 weeks (336 days),  $\geq$  60 weeks (420 days),  $\geq$  72 weeks (504 days),  $\geq$  84 weeks (588 days),  $\geq$  96 weeks (672 days), etc. Multiple study drug holidays and/or interruptions per subject will be combined into one cumulative total duration of study drug holidays and/or interruptions for each subject.

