# 4.2.2.2. Incomplete Dates

If study drug end or restart dates are incomplete (month and year only), then the day for the computation of study drug interruption durations will be imputed as the 15th of the month. However, if the study drug end and restart dates occur in the same month and year and at least one is incomplete (month and year only), then an interruption duration of 15 days will be imputed. If study drug end and restart dates are completely missing or only year is available, data query is needed and no interruption duration will be imputed.

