## **Summary**

These analyses demonstrate that PBMC-associated concentrations of TFV-DP are anticipated to be at or above the threshold associated with HIV prevention in participants (50th percentile and above) approximately 16 days and 10 days after cessation of multiple-dose F/TAF or F/TDF, respectively. As such, on-treatment HIV infections will be defined in GS-US-412-2055 as HIV infections diagnosed after first dose date through the last dose date +16 days for F/TAF or + 10 days for F/TDF.

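### SAP 6.2.6 counts a resumer's whole dosing gap as on-treatment, although Appendix 7 supports only about 10 or 16 days off drug; a gap-censored version with one rule for both arms should be added

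*SAP*

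**What the plan says.** SAP 6.2.6 runs on-treatment time from first dose to the double-blind last dose date plus 10 days (F/TDF) or 16 days (F/TAF). Off-treatment events and follow-up are those "occurring greater than 10 days for (F/TDF) or 16 days (for F/TAF) after permanent discontinuation of study drug". The Summary of SAP Appendix 7 gives the same rule: "HIV infections diagnosed after first dose date through the last dose date +16 days for F/TAF or + 10 days for F/TDF".

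Two definitions decide what this means for someone who stops and restarts. SAP Section 3 takes permanent discontinuation to be premature discontinuation or "completion of study drug and regardless of any gaps in continuous dosing". SAP 3.8.1 sets the double-blind last dose date as "the latest of the blinded study drug end dates (administering ≥1 tablet per day) recorded on the Study Drug Administration eCRF form".

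The window lengths come from simulated drug levels. Appendix 7 expects the median participant to stay at or above the 40 fmol threshold for "approximately 16 days and 10 days after cessation of multiple-dose F/TAF or F/TDF, respectively". It says nothing about gaps that are followed by resumption.

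The documents foresee resumption. SAP 4.2.2.1 reports the "percentage of subjects with study drug holidays and/or other study drug interruptions for specified periods". Protocol 6.8 sets HIV testing before restart after more than 14 consecutive days off drug. On post-exposure prophylaxis, Protocol 7.6.6 says: "Participants who complete their PEP regimen and wish to continue on study may resume with study medication". SAP 6.3 removes the adherence criterion from the per-protocol set, so interrupters stay in this analysis.

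**The concern.** SAP 6.2.6 is the plan's check on what happens to the rate ratio once off-drug time and infections are set aside. For participants who resume, it does not set that time aside. Their gap lies wholly before the latest dosing end date, so it counts as protected time whatever its length.

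The same definitions treat like cases unlike. Someone found infected at the end of a gap does not restart. The last dose then stays before the gap, and the infection falls outside the window. Someone uninfected restarts, and the identical gap becomes on-treatment follow-up. Off-drug time enters the denominator while many off-drug infections leave the numerator.

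Non-study PrEP has a parallel hole. SAP 6.2.6 excludes it only where use reaches past permanent discontinuation, so PrEP started and stopped within a gap is kept.

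At stake are the on-treatment rates. These feed the rate-ratio sensitivity analysis and also the per-protocol rows of Appendix Table 5, where each arm's rate is set against a predicted rate without PrEP. A rate that is too low flatters that comparison.

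**Working it through.** **1. The plan's own window lengths.** Inputs are from Appendix 7: threshold 40 fmol, mean troughs 434.0 or 430.2 (F/TAF) and 76.4 or 100.0 (F/TDF), half-lives 100–115 h (F/TAF) and 106–132 h (F/TDF). Shortcut: days = half-life × log2(trough/40) / 24.
- F/TAF: 14.3 to 16.5 days (up to 17.5 if the trough is 24 h after the last dose), consistent with 16.
- F/TDF: 4.1 to 7.3 days (up to 8.3), short of 10.

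The simulated median curve is not shown, so the F/TDF shortfall is only noted. The steps below take 10 and 16 days as given.

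**2. What a gap adds.** Days counted beyond the cover = 7 × weeks − 10 (F/TDF) or 7 × weeks − 16 (F/TAF). This follows from the text without assumptions.

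| Gap | F/TDF | F/TAF |
|---|---|---|
| 4 weeks | 18 | 12 |
| 12 weeks | 74 | 68 |
| 24 weeks | 158 | 152 |
| 48 weeks | 326 | 320 |

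The gap lengths are examples; the documents report none.

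**3. The one-sidedness, on a 24-week (168-day) gap in the F/TDF arm.**
- Infected in the gap, rapid retest positive: no restart (Protocol 6.8). Follow-up ends 10 days after the last pre-gap dose. A diagnosis after that is excluded.
- Not infected, restarts: all 168 days count.

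In the F/TAF arm the first participant contributes 16 days after the last dose and the second again 168.

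**4. Effect on a rate (illustration).** Assume 2500 per arm and 2 years, so 5000 person-years (SAP 1.3.1). Assume a fraction f has one gap of w weeks, and no gap infection is kept. Measured from day 17 off drug in both arms, the surplus share of person-time is s = 2500 × f × (7w − 16) / 365.25 / 5000. The reported rate is (1 − s) times the gap-censored rate.
- f = 2%, w = 4: 50 × 12 / 365.25 = 1.6 person-years, s = 0.03%.
- f = 10%, w = 12: 250 × 68 / 365.25 = 46.5 person-years, s = 0.93%. A rate of 1.44 per 100 person-years would be reported as 1.43.
- f = 20%, w = 48: 500 × 320 / 365.25 = 438.1 person-years, s = 8.8%. A rate of 1.44 would be reported as 1.31.

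**5. Effect on the rate ratio (illustration).** With equal gap shares the factor (1 − s) cancels. With 12-week gaps in 10% of one arm and 20% of the other, person-time after censoring is 5000 − 46.5 = 4953.5 and 5000 − 93.1 = 4906.9. Censoring then multiplies the ratio by 4906.9 / 4953.5 = 0.991, or by 1.009 if the arms are swapped.

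**The case against.** The strongest reply is that this is a stated convention. Appendix 7 and 6.2.6 agree word for rule, and the SAP counts through interruptions elsewhere, for example in duration of exposure (4.2.1) and treatment-emergent events (7.1.5.1). Section 6.3 openly drops the adherence criterion, and adherence is described separately by interruption length, pill count and self-report (4.2.2, 4.2.3). Part of this stands: the rule is deliberate and applied consistently. But the 10 and 16 days rest on a drug-level argument, and that argument does not reach week 12 of a gap. Describing interruptions elsewhere does not remove them from these rates.

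Three further points stand.
- The text of SAP 6.2.8 is absent from the file, although 6.2.7 cites a 6.2.8.1. A similar analysis there cannot be excluded.
- The sponsor had already unblinded for the primary analysis (SAP Section 1), so any new definition is post hoc.
- The duration bands in 4.2.2.1, which run to 96 weeks or more, are cumulative totals per participant. A reader might take them as evidence of single gaps that long; they are not.

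A reader might also infer that infections acquired in gaps are kept and pull the ratio toward 1, making noninferiority too easy to show. The documents do not support that strength. Testing continues off drug (Protocol 6.3), confirmed infection stops drug (6.11), and gaps over 14 days call for HIV samples before restart (6.8). A gap infection is kept only if dosing restarts before it is recognised, for example after a negative rapid test with central results pending. No figure for how often this happens is given.

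**Conclusion.** The point holds as a mismatch between the rule in 6.2.6 and its rationale in Appendix 7, with a one-sided treatment of gaps that tends to lower the on-treatment rates. That much needs no assumption beyond some participants resuming after gaps longer than the washout.

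The size is unknown, because the documents give no gap frequency. Under the illustrative inputs above, the rates fall by between 0.03% and 8.8%, and by about 1% in the middle case. The rate ratio moves by about 1% even if one arm has twice as many gaps as the other. The analysis carries no decision: the conclusion rests on the full analysis set (SAP 6.2.5), which is unaffected. This is an improvement to consider, not a threat to the trial's conclusion.

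A reader might go further and call the 10-day F/TDF window wrong, since the printed mean troughs and half-lives do not by themselves give 10 days. The documents do not establish that. The window is read from a simulated median curve that is not shown, and log-normal medians derived from the printed coefficients of variation fall short of the stated window in both arms (11.8–14.8 days for F/TAF, 2.4–5.9 for F/TDF).

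**What to change.** Add to SAP 6.2.6 a gap-censored version, alongside the planned one, with the same rule in both arms:
- Treat any recorded interruption longer than 16 days as off-treatment from day 17 after the last dose before the gap.
- Resume person-time and event eligibility together, at the first negative central HIV test on or after restart. Protocol 6.8 already calls for central samples before restart after gaps over 14 days, so this test should be available at restart.
- Exclude non-study PrEP time within those gaps.
- Carry the result into the per-protocol rows of Appendix Table 5.

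The common threshold matters. With arm-specific washouts, a gap of 11–16 days would be censored for F/TDF only. Up to 14 days, no restart sample is called for, so re-entry could wait until the next scheduled central test, about 12 weeks later, and on-drug infections could be lost in that arm alone. SAP 4.2.2.2 creates the same trap. For some gaps with incomplete dates in one month, "then an interruption duration of 15 days will be imputed", which exceeds 10 days but not 16. The price of the common threshold is that days 11–16 of an F/TDF gap stay counted.

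The change needs SAP wording and programming only, using the gap dates already derived for 4.2.2. This sensitivity analysis loses a few events and person-years. The version must be labelled as added after the primary-analysis unblinding, and 6.2.8 should be checked first for an equivalent.
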